7.1 Screening Phase

Screening procedures will be performed up to 28 days before Cycle 1 Day 1, unless otherwise specified. All subjects must first read, understand, and sign the IRB-approved informed consent form (ICF) before any study-specific screening procedures are performed. After signing the ICF, completing all screening procedures, and being deemed eligible for entry, subjects will be enrolled in the study. Procedures that are performed prior to signing the ICF and are considered standard of care may be used as screening assessments if they fall within the 28 day screening window.

The following procedures will be performed during the Screening Phase:

- Informed consent
- Review of eligibility criteria
- Medical history and demographics
- Record the Follicular Lymphoma International Prognostic Index (FLIPI) score
- Record tumor burden (GELF criteria)
- Review of AEs and concomitant medications

- Complete physical exam
- ECOG performance status
- Vital signs, weight, and height
- 12 lead ECG
- Imaging by CT/PET/or MRI
- Unilateral bone marrow aspirate and biopsy (can be done within 90 days of study entry)
- Clinical laboratory tests for:
 - Hematology (CBC with differential)
 - Serum chemistry (electrolytes [Na, K, Cl, bicarbonate, Ca], glucose, blood urea nitrogen [BUN], creatinine, alkaline phosphatase, AST, ALT, total protein, albumin, total bilirubin, lactate dehydrogenase [LDH], β 2-microglobulin), uric acid
 - Coagulation (PT/INR, aPTT)
 - Serum pregnancy test (for women of childbearing potential only) will be performed 10-14 days prior to writing an initial prescription for lenalidomide and again 24 hours prior to writing an initial prescription for lenalidomide.
 - Hepatitis serologies (hepatitis B surface antigen [HBsAg], hepatitis B core antibody [anti-HBc, hepatitis C antibody])
 - HIV 1 and 2 antibody
 - TSH
 - Determination of creatinine clearance (modified Cockcroft-Gault estimate) utilizing actual body weight
- Optional research tumor sample collection, fresh (for patients undergoing a biopsy as part of standard clinical practice for patients who provide consent) or archival (paraffin embedded).

7.2 Treatment Phase

7.2.1 Cycle 1/Day 1

Subjects who are deemed eligible will return to the clinic on Cycle 1, Day 1. The following procedures will be performed on Day 1:

Pre-Dose

- Confirmation of eligibility
- Complete physical exam
- ECOG performance status
- Vital signs and weight
- Clinical laboratory tests for:
 - Hematology
 - Serum chemistry
 - Determination of creatinine clearance (modified Cockcroft-Gault estimate) utilizing actual body weight
- Research laboratory blood sample collected pre-dose for:

Proprietary Information of MD Anderson

- Biomarkers
- Review of AEs and concomitant medications
- Dispense ibrutinib and lenalidomide

Dosing and Post-Dose

- In-clinic administration of ibrutinib
- In-clinic administration of rituximab
- In-clinic administration of lenalidomide

7.2.2 Cycle 1/Day 8

The following procedures will be performed on Cycle 1, Day 8 (± 2 days)

Pre-Dose

- Complete physical exam
- ECOG performance status
- Vital signs and weight
- Clinical laboratory tests for:
 - Hematology
 - Serum chemistry
 - Determination of creatinine clearance (modified Cockcroft-Gault estimate) utilizing actual body weight
- Review of AEs and concomitant medications

Dosing

- In-clinic administration of rituximab

7.2.3 Cycle 1/Day 15

The following procedures will be performed on Cycle 1, Day 15 (± 2 days)

Pre-Dose

- Complete physical exam
- ECOG performance status
- Vital signs and weight
- Clinical laboratory tests for:
 - Hematology
 - Serum chemistry
 - Determination of creatinine clearance (modified Cockcroft-Gault estimate) utilizing actual body weight
- Review of AEs and concomitant medications
- Research laboratory blood sample collected for:
 - Biomarkers
-

Proprietary Information of MD Anderson

Dosing

- In-clinic administration of rituximab

7.2.4 Cycle 1/Day 22

The following procedures will be performed on Cycle 1, Day 22 (± 2 days)

Pre-Dose

- Complete physical exam
- ECOG performance status
- Vital signs and weight
- Clinical laboratory tests for:
 - Hematology
 - Serum chemistry
 - Determination of creatinine clearance (modified Cockcroft-Gault estimate) utilizing actual body weight
- Review of AEs and concomitant medications

Dosing

- In-clinic administration of rituximab

7.2.5 Cycle 2/Day 1

The following procedures will be performed on Cycle 2, Day 1 (± 2 days)

- Complete physical exam
- ECOG performance status
- Vital signs and weight
- Clinical laboratory tests for:
 - Hematology
 - Serum chemistry
 - Determination of creatinine clearance (modified Cockcroft-Gault estimate) utilizing actual body weight
- Review of AEs and concomitant medications
- Drug accountability
- Dispense ibrutinib and lenalidomide
- Research laboratory blood draw
 - Biomarkers

Dosing

- In-clinic administration of rituximab

7.2.6 Cycle 2/Day 15

The following procedures will be performed on Cycle 2, Day 15 (± 2 days)

Proprietary Information of MD Anderson

- Complete physical exam
- ECOG performance status
- Vital signs and weight
- Clinical laboratory tests for:
 - Hematology
 - Serum chemistry
 - Determination of creatinine clearance (modified Cockcroft-Gault estimate) utilizing actual body weight
- Review of AEs and concomitant medications

7.2.7 Cycle 3/Day 1 and every 4 weeks until Treatment Termination

Visits will be performed every 4 weeks (\pm 2 days) starting at Cycle 3, Day 1. Visit windows are relative to Day 1 visit date. The following procedures will be performed:

- Complete physical exam
- ECOG performance status
- Vital signs and weight
- Clinical laboratory tests for:
 - Hematology
 - Serum chemistry
 - Determination of creatinine clearance (modified Cockcroft-Gault estimate) utilizing actual body weight
- Review of AEs and concomitant medications
- Drug accountability
- Dispense ibrutinib and lenalidomide
- CT/PET/or MRI on Cycle 4/Day 1 (\pm 7 days) and Cycle 7/Day 1 (\pm 7 days) only
- Research laboratory blood draw (Cycle 7/Day 1 only)
 - Biomarkers

Dosing

- In-clinic administration of rituximab

7.2.8 Early Treatment Termination Visit

The early treatment termination visit should be performed at any time during the study (\pm 14 days), if based on the clinical evaluation, the investigator suspects PD, or if the subject discontinues treatment for any other reason outlined in Section 5.6. If the subject comes in for a regular study visit and the investigator wants to discontinue treatment at that time, the regular visit will become the termination visit. Any additional procedures that would be performed for the regular study visit should be performed for the treatment termination visit. Adverse events and hospitalizations will be recorded up to 30 days after the last dose of study drugs.

The following procedures will be performed:

- Complete physical exam
- ECOG performance status
- Vital signs and weight
- Clinical laboratory tests for:
 - Hematology
 - Serum chemistry
 - TSH
- Research laboratory tests for:
 - Biomarkers
- Review of AEs and concomitant medications
- Drug accountability
- CT/PET/or MRI
- Optional tumor tissue biopsy to document PD (Research biomarker assessment)

7.2.9 End of Treatment Visit

The end of treatment visit will occur approximately 4 weeks (± 14 days) from last dose of study drugs (end of cycle 12) for patients who complete the planned study treatment. Adverse events and hospitalizations will be recorded up to 30 days after the last dose of study drugs.

The following procedures will be performed:

- Complete physical exam
- ECOG performance status
- Vital signs and weight
- Clinical laboratory tests for:
 - Hematology
 - Serum chemistry
 - TSH
- Research laboratory tests for:
 - Biomarkers
- Review of AEs and concomitant medications
- Drug accountability
- CT/PET/or MRI

7.2.10 Response Evaluations

Response Evaluation visits will be performed at the following timepoints:

- At approximately Cycle 4, Day 1 and cycle 7, Day 1 (± 7 days).
- At the End of treatment visit or at the early treatment termination visit (± 2 weeks).
- Every 12 weeks (± 2 weeks) during the follow up phase for the first 4 assessments and then every 24 weeks until the subject exhibits disease progression (± 4 weeks).
- The following procedures will be performed in conjunction with standard visits as follows:
 - Radiologic exam by CT, PET/CT, or MRI scan

Proprietary Information of MD Anderson

- Bone marrow biopsy and/or aspirate with assessment of MRD, to be done once to confirm CR if marrow was involved with lymphoma at screening
- Overall response assessment
- Research laboratory blood samples (when subject achieved CR and/or at PD)

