5.3 Treatment Schedule

Patients will receive 12 cycles of lenalidomide, 15mg daily on days 1-21 of cycle 1, and 20mg daily on days 1-21 (± 2 days) of cycles 2 through 12. Cycles will be 28 days in length. Patients will receive rituximab, 375mg/m² on days 1, 8 (± 2 days), 15 (± 2 days), and 22 (± 2 days) of cycle 1, and day 1 (± 2 days) of cycles 2 through 12. Patients will receive ibrutinib 560mg daily, starting on day 1 of cycle 1 and continued through 12 cycles. Therapy is continued for 12 cycles or until disease progression, unacceptable toxicity, or voluntary withdrawal.

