7.3 Follow-up Phase

The follow up period will start at the end of treatment visit (after cycle 12) Patients will be followed every 12 weeks (\pm 2 weeks) for the first year and then every 24 weeks (\pm 4 weeks) up to the end of the follow up period, 3 years after the last subject's last study drug dose.

For patients who have completed treatment the follow up assessments will include:

- Physical exam including vital signs and ECOG PS
- Clinical laboratory tests for hematology and serum chemistry
- Second primary malignancy (SPM)
- Adverse events and hospitalization up to 30 days after last study drug
- Overall survival
- Radiologic assessment (CT, PET/CT, or MRI)
- Research laboratory blood samples at PD only.

For patients who discontinue treatment due to progressive disease or relapse, follow up assessments will include:

- Overall survival
- Subsequent anti-lymphoma therapy (including the time of initiation of therapy and best response to first subsequent anti-lymphoma treatment utilized after discontinuation from this study)
- Adverse events and hospitalization up to 30 days after last study drug (Safety visit)
- SPM

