7.3.1 Survival Follow Up

Once subject progresses or starts use of alternative antineoplastic therapy (for subjects who have not withdrawn consent), they will be contacted approximately q 12 weeks (\pm 2 weeks) for 1 year and then q 24 weeks (\pm 4 weeks) from the last dose of study drug by clinic visit or telephone to assess survival and the use of alternative antineoplastic therapy and stem cell transplant. Subjects will be contacted until: death, consent withdrawal, lost to follow up, or study termination, whichever comes first.

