9.3.2.1 Analysis Methods

The primary analysis for all efficacy endpoints will be conducted based on the all treated population. PFS is defined as the time from the treatment start date (Cycle 1, Day 1) until the first date of objectively documented progressive disease or date of death from any cause. Patients will be censored at the last follow-up date if progression or death has not occurred during follow-up. If a patient has missing data (incomplete CT scan), all other available CT, PET/CT or MRI of the patient will be used for the analysis. Kaplan-Meier method will be used to estimate the PFS. Corresponding 95% CI will be summarized. Cox proportional hazards models will be used to assess the effects of patient prognostic factors on time-to-event endpoints. The final analysis will be performed when the last patient is followed for 3 years after last study drug dose.

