9.3.3 Secondary Efficacy Endpoints

- CR rate at 120 weeks (± 4 weeks) will be determined by the PI (Cheson, Lugano classification 2014). The number and percentage of subjects with a CR at 120 weeks will be tabulated.
- ORR (CR + PR) will be assessed by the investigator based on Cheson, Lugano 2014. The number and percentage of subjects with an ORR will be tabulated. The best ORR will be recorded.
- DOR will be measured from the time by which measurement criteria for CR or PR, whichever is recorded first, is met until death or the first date by which progressive disease is documented. Subjects who are progression free and alive at the time of clinical cut-off or have unknown

status will be censored at the last tumor assessment. Subjects with no baseline disease assessment will be censored on cycle 1, day 1. Non-responders will be excluded from the analysis for DOR. Kaplan-Meier methodology will be used to estimate event-free curves, median, and 95% CI.

- EFS will be measured from the date of cycle 1, day 1 to the date of first documented progression, transformation to diffuse large B-cell lymphoma, initiation of new anti-lymphoma treatment, or death. Kaplan-Meier methodology will be used to estimate event-free curves, median, and 95% CI.
- TTNT will be measured from the date of cycle 1, day 1 to the date of first documented administration of any anti-lymphoma treatment (chemotherapy, radiotherapy, immune therapy, radioimmunotherapy, or other experimental therapy). Kaplan-Meier methodology will be used to estimate event-free curves, median, and 95% CI.
- OS will be measured from the date of cycle 1, day 1 to the date of death regardless of cause. For subjects who have not died, subjects will be censored at the time of last contact. Kaplan-Meier methodology will be used to estimate event-free curves, median, and 95% CI.

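### For an on-time completer, the only scan that can serve CR at 120 ± 4 weeks is due at week 124, the window's closing edge, and about half of its permitted dates fall outside

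*Combined protocol and SAP*

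**What the plan says.** The scan calendar has to be assembled from four places in the combined protocol and SAP.

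- Section 5.3: twelve cycles; "Cycles will be 28 days in length".
- Section 7.2.9: "The end of treatment visit will occur approximately 4 weeks (± 14 days) from last dose of study drugs (end of cycle 12".
- Section 7.3: "The follow up period will start at the end of treatment visit (after cycle 12".
- Section 7.2.10: response is assessed "Every 12 weeks (± 2 weeks) during the follow up phase for the first 4 assessments and then every 24 weeks". The 24-weekly scans carry ± 4 weeks. Footnote o of the flow chart (Section 13.1) repeats this schedule.

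The endpoint is in Section 9.3.3: "CR rate at 120 weeks (± 4 weeks) will be determined by the PI". Its time origin is not stated. The neighbouring time-to-event endpoints do state theirs: "PFS is defined as the time from the treatment start date (Cycle 1, Day 1" in Section 9.3.2.1 and "EFS will be measured from the date of cycle 1, day 1 to the date of first documented progression" in Section 9.3.3, with TTNT and OS counted the same way.

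Two flow-chart footnotes bear on patients who do not finish on time. Footnote b keeps patients who stop early without progression on the follow-up schedule, without saying when that schedule starts for them. Footnote c lets cycles lengthen for toxicity but exempts response assessment from the shift.

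**The concern.** The visit window and the endpoint window were set separately, and they overlap only in part. A patient and a site can keep every visit within its permitted dates and still have no scan inside the weeks over which CR is to be read.

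CR at 120 weeks is the first-listed secondary efficacy endpoint, and the Background presents it as a surrogate endpoint. The default denominator is the all-treated population, planned at 60, so each patient classed differently moves the rate by 1/60, about 1.7 percentage points. The plan does not say how a scan just outside the window is to be counted. That choice would be made at analysis, with the responses known.

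**Working it through.** The documents state no week for the fifth follow-up scan, so there is no plan figure to reproduce. The check is calendar arithmetic in days.

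**Assumptions.** Week 0 is Cycle 1 Day 1, taken as the origin of the 120 weeks because PFS, EFS, TTNT and OS all start there. Follow-up scans are counted from the EOT visit, as Section 7.3 indicates. The patient completes 12 cycles without delay.

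**Calendar**

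1. End of cycle 12: 12 × 28 days = 336 days = week 48.
2. EOT visit: 48 + 4 = week 52; with ± 14 days, weeks 50 to 54.
3. Follow-up scans 1 to 4: 52 + 12, 24, 36, 48 = weeks 64, 76, 88, 100.
4. Scan 5: 100 + 24 = week 124. Scan 6: 124 + 24 = week 148.
5. Endpoint window: 120 ± 4 = weeks 116 to 124, i.e. days 812 to 868.

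**Which scan can serve.** Over EOT weeks 50 to 54, scan 4 (± 2 weeks) spans weeks 96 to 104 and scan 6 (± 4 weeks) spans weeks 142 to 154. Neither reaches 116 to 124, so only scan 5 can.

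**Permitted dates of scan 5 inside the window.** The visit window has 28 + 1 + 28 = 57 dates. The number inside is 868 − (7 × due week − 28) + 1. For EOT week 52 this is 868 − 840 + 1 = 29.

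| EOT week | Scan 5 due | Permitted weeks | Dates inside | Dates outside |
|---|---|---|---|---|
| 50 | 122 | 118–126 | 43/57 | 14/57 (25%) |
| 51 | 123 | 119–127 | 36/57 | 21/57 (37%) |
| 52 | 124 | 120–128 | 29/57 | 28/57 (49%) |
| 53 | 125 | 121–129 | 22/57 | 35/57 (61%) |
| 54 | 126 | 122–130 | 15/57 | 42/57 (74%) |

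An EOT visit one day after week 52 already puts the due date one day past the window.

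**Sensitivity.** If the last dose falls on the last day of cycle 12 (day 335 from the origin), EOT moves one day earlier and 30 of 57 dates are inside. If scans were counted from the last dose at week 48, they would fall at weeks 60, 72, 84, 96 and 120. Scan 5 would then be permitted at 116 to 124, and all 57 dates would be inside.

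**Patients off the nominal calendar** (assuming scans run from the actual EOT or termination visit):

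- Delayed completer with EOT at week E: no permitted date in the window if scan 5 opens too late (E + 72 − 4 > 124) and scan 4 closes too early (E + 48 + 2 < 116). That is 56 < E < 66.
- Early stopper with termination at week t: none if t + 72 + 4 < 116 and t + 96 − 4 > 124, so 32 < t < 40; or if t + 96 + 4 < 116 and t + 120 − 4 > 124, so 8 < t < 16.

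**The case against.** **The anchor could be the last dose.** The windows would then match exactly. Section 7.3.1 does count "from the last dose of study drug by clinic visit or telephone to assess survival", but that rule covers contacts after progression or new therapy, not scans. Section 7.3 starts follow-up at the EOT visit. The origin of the 120 weeks is unstated, and that part of the objection stands: the conflict rests on a stated assumption.

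**The plan already handles missing scans.** Section 9.3.2.1 falls back on other available imaging, and its opening sentence covers all efficacy endpoints. Its trigger, however, is an incomplete CT within the PFS method. It does not say whether a complete scan at week 126 is read as CR at 120 weeks; if it always were, the ± 4 weeks would do nothing. Section 7.3.2 asks that missed evaluations be made up near their scheduled date. For EOT at week 52 that date counts, but the section does not reconcile the two windows.

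**The clinical concept is loose.** The Background names 120 weeks or 30 months for this endpoint, and 30 months is about week 130 (30 × 30.44 / 7). A scan at weeks 125 to 128 is still within that concept. This limits the consequence, but Section 9.3.3 chose ± 4 weeks.

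**Stronger readings to avoid.** A reader might infer that any EOT visit after week 52 puts the scan outside the window. That is true only of a scan taken on its due date: at EOT week 53 or 54, 22 or 15 of the 57 permitted dates remain inside. A reader might also infer that half the patients will lose their CR assessment. Shares of permitted dates are not probabilities; sites can book early, and the documents give no booking pattern.

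**Conclusion.** The point holds as a mismatch between two stated rules. It assumes Cycle 1 Day 1 as the origin and the EOT visit as the scan anchor. For an on-time completer with EOT at week 52, the one usable scan is due at the closing edge of the CR window, and 28 of 57 permitted dates miss it. Across EOT weeks 50 to 54 the share outside runs from about 25% to 74%.

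The consequence is limited. CR at 120 weeks is tabulated without a test. The primary endpoint, 2-year PFS, is a Kaplan-Meier estimate that does not use this window and is essentially unaffected. How far the CR rate could shift depends on booking and on a counting rule the plan does not give, so no loss is forecast. The change is worth making because it is cheap. The figures for delayed patients and early stoppers rest on a further assumption about their anchor and show only that the anchor needs stating.

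**What to change.** 1. In Section 9.3.3, state that the 120 weeks run from Cycle 1 Day 1.
2. In Section 7.2.10 and footnote o, schedule the fifth follow-up response assessment for on-time completers at week 120 ± 4 from Cycle 1 Day 1. Visit and endpoint windows then coincide and all permitted dates count.
3. For early stoppers and patients with delayed cycles, do not move scans. Reconcile footnotes b and c with Sections 7.2.9 and 7.3 on what anchors the scans, and use the existing scan nearest week 120.
4. State how an out-of-window scan is counted. Report how many patients had an in-window scan, how many had progression or death before the window, and how many had neither.

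**Cost.** No scan is added. With EOT at week 52, one scan moves 4 weeks earlier (2 to 6 weeks across EOT weeks 50 to 54). The interval before it becomes 120 − 100 = 20 weeks. The next becomes 148 − 120 = 28 weeks (26 to 30 across EOT weeks 50 to 54), unless the sixth scan also moves, for example to week 144.

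Early stoppers are left alone because moving their scans would open long imaging gaps. With termination at week 37, scans fall at weeks 85, 109 and 133, and moving 109 to 120 leaves 35 weeks without imaging. The price of using the nearest scan is that it may be due up to 12 weeks from week 120 (termination at week 12 or 36), which is why the count in item 4 is needed.

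**If the calendar cannot change,** widen the analysis window to weeks 116 to 130. This covers every permitted date for EOT weeks 50 to 54 (118 to 130). A window of 120 to 128 would fit only EOT week 52. This needs one sentence in Section 9.3.3 and no visit change, but the endpoint is then read over a longer interval.

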7.3 Follow-up Phase

The follow up period will start at the end of treatment visit (after cycle 12) Patients will be followed every 12 weeks (\pm 2 weeks) for the first year and then every 24 weeks (\pm 4 weeks) up to the end of the follow up period, 3 years after the last subject's last study drug dose.

For patients who have completed treatment the follow up assessments will include:

- Physical exam including vital signs and ECOG PS
- Clinical laboratory tests for hematology and serum chemistry
- Second primary malignancy (SPM)
- Adverse events and hospitalization up to 30 days after last study drug
- Overall survival
- Radiologic assessment (CT, PET/CT, or MRI)
- Research laboratory blood samples at PD only.

For patients who discontinue treatment due to progressive disease or relapse, follow up assessments will include:

- Overall survival
- Subsequent anti-lymphoma therapy (including the time of initiation of therapy and best response to first subsequent anti-lymphoma treatment utilized after discontinuation from this study)
- Adverse events and hospitalization up to 30 days after last study drug (Safety visit)
- SPM

